Supporting document SOP PM01 – Doc PM3004.03

Estetra Post Authorisation study information

Title	International Active Surveillance Study: Native Estrogen Estetrol (E4) Safety Study (INAS-NEES)
Protocol version identifier	V04-00
Date of last version of protocol	Not applicable
EU PAS register number	Not yet registered
Active substance	Pharmacotherapeutic group: Sex hormones and modulators of the genital system, progestogens, and estrogens, fixed combinations, Anatomical Therapeutic Chemical Classification System (ATC) code: G03AA18
	Active substances: drospirenone and estetrol
Medicinal product	Drospirenone 3 mg/estetrol 14.2 mg film-coated tablets
Product reference	Lydisilka: H0005382 Drovelis: H0005336
D. I. I.	Lydisilka: EMEA/H/C/005382
Procedure number	Drovelis: EMEA/H/C/005336
	Estetra SRL [name] Belgium
Marketing authorisation holder(s)	Gedeon Richter Plc [name] Hungary
Joint PASS	Yes
Research question and objectives	The primary objective of the study is to characterize and compare the risks of E4/Drospirenone (DRSP) with levonorgestrel-containing combined oral contraceptives (EE/LNG) in a study population that is representative of the actual users of these

Supporting document SOP PM01 – Doc PM3004.03

	preparations. The main clinical outcome of interest is
	venous thromboembolism (VTE), specifically deep venous thrombosis (DVT) and pulmonary embolism (PE). Secondary objectives include measuring the occurrence of unintended pregnancy, assessing the risk of arterial thromboembolism (ATE), describing the drug utilization pattern, describing the baseline risk profile for VTE and ATE, and investigating outcomes associated with foetal exposure to E4/DRSP.
Country(-ies) of study	Europe (Germany, Poland, Czech Republic, the United Kingdom, Hungary, Italy, France, Spain, other (TBD)), USA and Brazil. A complete list is available in Annex 1
Author(s)	[name] ZEG Berlin [name] Germany

Marketing authorisation holder(s)

Marketing authorisation holder (s)	Estetra SRL [name] Belgium Gedeon Richter Plc [name] Hungary
MAH contact person	[name] Head of Clinical Operations Estetra SRL

Supporting document SOP PM01 – Doc PM3004.03

Table of contents

Es	tetra	Post Authorisation study information	1
Ta	ble of	f contents	3
Li	st of a	bbreviations	5
Re	espons	sible parties	8
1.		Abstract	9
2.		Amendments and updates	12
3.		Milestones	12

The combined oral contraceptive (COC) containing estetrol (E4) and drospirenone (DRSP) (E4/DRSP) is a novel oral contraceptive containing a fixed dose of E4 (14.2 mg) and DRSP (3 mg). E4 is a natural oestrogen only produced during pregnancy by the foetal liver. When combined with the progestin DRSP, ovulation is inhibited. The E4/DRSP combination may have less impact on hepatic and haemostasis parameters in comparison to combinations of ethinyl estradiol (EE) and levonorgestrel (LNG) or EE and DRSP. Yet, it is unknown whether this regimen has an impact on the cardiovascular risk associated with the use of hormonal contraceptives.

Research question and objectives

The primary objective of the study is to characterize and compare the risks of E4/DRSP with EE/LNG, in a study population that is representative of the actual users of these preparations. This includes an estimate of the absolute risk of rare serious adverse outcomes. The main clinical outcome of interest is venous thromboembolism (VTE), i.e., deep venous thrombosis (DVT) of the lower extremities and pulmonary embolism (PE). Secondary objectives include measuring the occurrence of unintended pregnancy, assessing the risk of arterial thromboembolism (ATE), describing the drug utilization pattern, describing the baseline risk profile for VTE and ATE, and investigating outcomes associated with foetal exposure to E4/DRSP.

Study design

Multinational, comparative, prospective, active surveillance study that follows two cohorts. The cohorts consist of new users (starters¹ and restarters²) of two different groups of hormonal

First-ever user of a COC

User who restarts hormonal contraceptive use with a COC (same COC as before or new COC) after an intake break of at least two months.

Supporting document SOP PM01 - Doc PM3004.03

contraceptives: E4/DRSP and EE/LNG. The study is taking a non-interventional³ approach to provide comprehensive information on these treatments in a routine clinical practice setting. Study participants will be enrolled via an international network of COC-prescribing health care professionals (HCPs) and then followed up for one to two years. All outcomes of interest will be captured by direct contact with the study participants. Reported outcomes of interest will be validated via attending physicians and relevant source documents. The classification of outcomes of interest into 'confirmed' and 'not confirmed' will be verified by blinded independent adjudication.

Population

Approximately 101,000 study participants (50,500 E4/DRSP and 50,500 EE/LNG new users) will be recruited via a network of COC-prescribing health care professionals in Europe, the USA, and Brazil. All new users (starters and restarters) prescribed E4/DRSP or EE/LNG who are willing to participate may be eligible for enrolment in the study.

Variables

The variable to determine the primary endpoint is the occurrence of a new VTE (DVT of the lower extremities and PE) during follow-up, which will be compared between E4/DRSP and EE/LNG users. Variables to determine the secondary endpoints include the occurrence of unintended pregnancies, ATE, and outcomes associated with foetal exposure to E4/DRSP. Variables to characterize the baseline risk profile of users are baseline population characteristics, socio-economic factors, parameters of reproductive, contraceptive, and medical history, and concomitant medication.

Data sources

This is a field study that entails exposure to COCs and the occurrence of clinical outcomes of interest by completing questionnaires at baseline (study entry) and follow-up (at 6-, 12-, 18-, and 24-months post-baseline), in addition to potential confounding factors and potential effect modifiers. Medical confirmation of the occurrence of a clinical outcome of interest will be sought from the attending HCP and/or study participant (e.g., diagnostic report, discharge letter). All documents exchanged between ZEG and the MAHs will be in English.

Study size

The study is sufficiently powered to show non-inferiority of E4/DRSP compared to EE/LNG assuming that the VTE risk among E4/DRSP users is not higher than among EE/LNG users. For this purpose, a total of 101,000 women (50,500 E4/DRSP users and 50,500 EE/LNG users) will be recruited and followed up taking into account treatment adherence, treatment stopping/switching, and lost to follow-up (LTFU)/dropout. Sample size calculations assuming an incidence of 10 VTEs per 10,000 woman-years (WY) show that approximately 150,000 WY of observation is statistically sufficient (power =80%, α =0.05) to exclude a 1.5-fold VTE risk for E4/DRSP users compared to EE/LNG users.

³ Specifically, 1) all new users of E4/DRSP or EE/LNG are eligible for enrollment if they give their informed consent; and 2) recruitment of study participants should not influence the physician's prescribing, diagnostic, or therapeutic decisions.

Supporting document SOP PM01 - Doc PM3004.03

Data analysis

The final analyses will include both an "as-treated" (AT) and an "intention-to-treat" (ITT) analysis. All eligible women will be assigned to the ITT and AT population at baseline. Only women with follow-up information will be considered for longitudinal analysis. Women who never started their prescribed baseline medication will be considered in the ITT analysis but excluded from the AT analysis. Population characteristics, e.g., socio-economic factors, parameters of reproductive, contraceptive history, and medical history, will be summarized descriptively and used to estimate the probability of treatment differences. Inverse probability of treatment weighting combined with time-to-event analysis of VTE will be carried out based on the extended Cox model to calculate hazard ratios (HR) with 95% confidence intervals. The null hypothesis to be tested is HR of VTE ≥1.5 (i.e., the VTE HR for E4/DRSP vs. EE/LNG is higher than or equal to 1.5). The alternative hypothesis is HR of VTE <1.5.

Milestones

Data collection is expected to start Q4/2022 after EMA approval of protocol and medical drug commercially available and is anticipated to end Q4/2028 after the start of data collection. The final study report will be available in Q2/2029.

Supporting document SOP PM01 - Doc PM3004.03

2. Amendments and updates

Number	Date	Section of study protocol	Amendment or update	Reason
None				

3. Milestones

Milestone	Planned date
Global Ethics Approval	Q4/2022
Registration in the EU PAS register	Q4/2022
Start of study	Q4/2022
Start of data collection (First Patient First Visit)	Q1/2023
Last regular follow-up ¹	Q3/2027
End of data collection (Last Patient Last Follow-Up)	Q3/2028
Annual report(s) ²	Annually (First report: Q2/2023)
Final report of study results	Q2/2029

EMA=European Medicines Agency, MA=Marketing Authorization, PRAC=Pharmacovigilance Risk Assessment Committee ¹Assumes last 20% of study participants followed for 12 months only.

4. Rationale and background

E4/DRSP is a novel oral contraceptive containing a fixed dose of E4 (14.2 mg) and DRSP (3 mg) which is taken for 24 days followed by 4 days of placebo. E4 is a natural estrogen, only produced during pregnancy by the foetal liver. When combined with the progestin DRSP, ovulation is inhibited. The E4/DRSP combination may have less impact on hepatic and haemostasis parameters in comparison to combinations of DRSP with ethinyl estradiol (EE) and ethinyl estradiol/levonorgestrel combination (EE/LNG) [1–3].

Clinical experience suggests that serious clinical outcomes are rare when using COCs. [4, 5] One of the most serious adverse clinical events that have been linked to the use of COCs is VTE. However, the statistical power to detect and observe rare (incidence<0.01%) adverse events (AEs) with a certain precision in clinical trials is limited.

There is preliminary evidence that E4/DRSP has less influence on haemostasis compared to EE/DRSP. [6] Therefore, it is conceivable that E4/DRSP might be associated with a lower risk of VTE compared to an EE-containing COC. However, robust estimates of the risk of VTE associated with E4/DRSP are not available. As part of the Risk Management Plan for the novel

²To be harmonized with the Periodic Safety Update Reports (PSURs), where applicable

Supporting document SOP PM01 - Doc PM3004.03

COC containing E4/DRSP, Estetra and Gedeon Richter have committed to conducting a non-imposed, category 3, Post-authorization Safety Study (PASS) according to DIR 2001/83/EU art 107m). The PASS will be conducted to assess the risk of VTE in 'real world' users of E4/DRSP, as well as the risk of ATE and unintended pregnancy.

The European Active Surveillance (EURAS) study and similar studies (such as INAS-SCORE⁴, INAS-OC⁵ and PRO-E2⁶) have demonstrated that large, comparative, cohort studies are suitable for (1) safety monitoring of contraceptives, (2) reliable identification of relevant clinical outcomes, and (3) providing robust estimates of their incidence. The proposed study has a similar design to the PRO-E2 with few modifications due to country and product-specific characteristics.

5. Research question and objectives

The main research question of the study is to assess the thromboembolic risk associated with the use of E4/DRSP compared to EE/LNG in a study population that is representative of the actual users of the individual preparations. This includes an estimate of the absolute risk of rare serious adverse outcomes as defined below.

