Therefore, with the assumption that 150,000 WY is the feasibility limit for a prospective, non-interventional study, it is possible to construct alternative scenarios based on a lower overall VTE incidence rate of 7.0 VTE/10,000 WY (Table 2).

Table 2: Sample size alternatives based on various assumptions.

Inc. COC _{LNG}	Inc. E4/DRSP	HR ₀	HR _{ni}	Expected #VTE	WY _{Total}	Power (%)
0.001	0.001	1	1.5	151	150,426	80%
0.0007	0.0007	1	2	105	150,000	97%
0.0007	0.0007	1	1.65	105	150,000	82%

Inc.: incidence of VTE; COC_{LNG}: Levonorgestrel-containing combined oral contraceptive; E4/DRSP: Estetrol/Drospirenone; HR: Hazard ratio; #VTE: Number of venous thromboembolisms; WY: Women-year

ZEG Berlin

Estetra Study Protocol

Supporting document SOP PM01 - Doc PM3004.03

Line 2 and 3 show that with a lower overall incidence of 7.0 VTE/10,000 WY, and pre-specified 150,000 WY of observation, the study would still have 97% power to exclude a 2.0-fold risk, and >80% power to exclude a 1.65-fold risk.

As an additional comment, our current working hypothesis is that E4/DRSP will have a slightly lower risk of VTE compared to currently available COCs, including EE/LNG. This assumption is based on results from clinical trials and comparative studies on coagulation biomarkers:

- The observed VTE incidence from the pooled Phase 2-3 E4 clinical program was 2.8 VTE/10,000 women (95% CI 0.7 15.6), with a 95% confidence interval based on Poisson distribution.
- The VTE incidence rate, in view of 2,735 WY of exposure, was 3.7 VTE/10,000 WY (95% CI: 0.9 20.4).
- Haemostasis parameters were investigated in Study MIT Es0001-C201 which concluded that E4/DRSP 15/3 mg was associated with -
 - Less resistance to activated Protein C (APC) than EE/LNG (change from baseline: +30% versus +165%)
 - Decreased change from baseline in F1+2 as compared with EE/LNG (+23% versus +71%)
 - o No statistically significant changes from baseline in coagulation inhibitors.
 - o No effect on soluble E-selectin

and therefore, a more neutral haemostatic profile.

- Overall haemostasis results indicate that E4/DRSP 15/3 mg has less effect on haemostatic parameters compared with EE/LNG 0.03/0.15 mg, and also less than observed with the COCs containing E2 [8, 9] and E2V. [10, 11]
- The VTE adjusted hazard ratio of E2V versus EE/LNG was observed as 0.4 (95% CI 0.2-1.1) in the INAS-SCORE PASS. [12].

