6.7. Data analysis

6.7.1. Statistical analysis

Based on available data and pharmacological considerations, the *a priori* assumption is that the use of E4/DRSP is not associated with an increased risk of VTE compared to EE/LNG. Therefore, a non-inferiority design to investigate the VTE risk of E4/DRSP has been deemed appropriate. The primary analysis will be based on the comparison of the upper confidence limit for the point estimate of the VTE hazard ratio (HRVTE) with a predefined non-inferiority limit. The null hypothesis to be tested is: HRVTE \geq 1.5 (i.e., the VTE hazard ratio for E4/DRSP vs. EE/LNG is higher than or equal to 1.5). The alternative hypothesis is: HRVTE<1.5.

The final analyses will include both an "as-treated" (AT) and an "intention-to-treat" (ITT) analysis. All eligible women will be assigned to the ITT and AT population at baseline. Only women with follow-up information will be considered for longitudinal analysis (e.g., distribution of outcomes over time, incidence rates, time-to-event). Women who never started their prescribed baseline medication will be considered in the ITT analysis but excluded from the AT analysis.

Baseline population characteristics, e.g., socio-economic factors, parameters of reproductive, contraceptive history, and medical history will be described as baseline risk profiles and considered as time-invariant continuous or categorical variables to describe sources of risk and confounding in the analysis. Inverse probability of treatment weighting (IPTW) using propensity scores (PS) will be considered to correct for covariate imbalances between cohorts. Logistic regression will be applied as a common model for the estimation of PS. The adequacy of the PS model will be assessed by comparing absolute standardized differences between IPT-weighted synthetic cohorts. The average treatment effect of E4/DRSP on the risk of VTE compared to EE/LNG will be obtained from time-to-event analysis using an application of the extended (weighted) Cox model. The observed HR_{VTE} between users of E4/DRSP and EE/LNG will be provided with 95% confidence intervals.

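### The powers in Tables 2 and 3 assume a one-sided 5% test, but the only interval named for the VTE hazard ratio is 95%; if its upper limit decides, headline power is about 70%, not 80%

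*Protocol*

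**What the plan says.** **Sample size.** The abstract (Study size) says that "approximately 150,000 WY of observation is statistically sufficient (power =80%, α =0.05) to exclude a 1.5-fold VTE risk". Section 6.5 repeats the claim with the same power and α. Neither place gives the sidedness. Table 2 lists powers of 80% (margin 1.5, 151 events, 150,426 WY), 97% (margin 2.0, 105 events) and 82% (margin 1.65, 105 events), all with a true hazard ratio of 1. Table 3 lists 92% (margin 1.5, true hazard ratio 0.8, 95 events). The text under Table 2 concludes that "the study would still have 97% power to exclude a 2.0-fold risk, and >80% power to exclude a 1.65-fold risk".

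**Decision rule.** Section 6.7.1 bases the primary analysis on the "comparison of the upper confidence limit for the point estimate of the VTE hazard ratio (HRVTE) with a predefined non-inferiority limit". The level of that limit is not given. The hypotheses are one-directional: "The null hypothesis to be tested is HR of VTE ≥1.5" against a ratio below 1.5.

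**Interval.** Two paragraphs later, 6.7.1 says that the observed hazard ratio "between users of E4/DRSP and EE/LNG will be provided with 95% confidence intervals". The abstract (Data analysis) says the same: "extended Cox model to calculate hazard ratios (HR) with 95% confidence intervals". The protocol does not mention a one-sided test, a 90% interval or a one-sided 95% limit.

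**The concern.** A two-sided 95% interval compared with a margin is a test at one-sided 2.5%. A sample size worked out at one-sided 5% matches the upper limit of a two-sided 90% interval. A reader who takes 6.7.1 in the ordinary way will compare the upper end of the reported 95% interval with 1.5, and the design does not have its stated power under that rule.

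Two things are at stake. The first is the probability of failing to show non-inferiority when the two products carry equal risk, which is 20% under one rule and about 30% under the other. The second is the conclusion itself, because the largest observed hazard ratio that passes differs between the two rules.

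**Working it through.** **Inputs, all from the protocol.** Allocation 1:1 (6.2). Margins, true hazard ratios, event counts and powers from Tables 2 and 3 (6.5). Incidence 10 per 10,000 WY for the main scenario (6.5). α = 0.05 and power 80% (abstract and 6.5).

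**Formulas (Schoenfeld, 1:1).**
- Events = 4 × (z_α + z_power)² / [ln(margin/HR)]²
- Power = Φ( ln(margin/HR) × √events / 2 − z_α )
- z_α = 1.645 for one-sided 5% (upper end of a two-sided 90% interval); z_α = 1.960 for one-sided 2.5% (upper end of a two-sided 95% interval); z_power = 0.842 for 80%.

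**Step 1: reproduce the protocol's own figure.** With z_α = 1.645 and margin 1.5, ln 1.5 = 0.4055 and events = 4 × (1.645 + 0.842)² / 0.4055² = 150.43, which rounds up to the stated 151. Dividing by 0.001 gives 150,425 WY against the stated 150,426. The sample size was therefore computed at one-sided 5%. With z_α = 1.960 the same formula gives 190.97, so 191 events.

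**Step 2: power in each row under both limits.** The middle column is ln(margin/HR) × √events / 2.

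| Row | Margin | True HR | Events | ln(margin/HR) × √events / 2 | Stated power | z = 1.645 | z = 1.960 |
|---|---|---|---|---|---|---|---|
| Table 2, line 1 | 1.5 | 1 | 151 | 2.491 | 80% | 80.1% | 70.2% |
| Table 2, line 2 | 2.0 | 1 | 105 | 3.551 | 97% | 97.2% | 94.4% |
| Table 2, line 3 | 1.65 | 1 | 105 | 2.566 | 82% | 82.1% | 72.8% |
| Table 3 | 1.5 | 0.8 | 95 | 3.063 | 92% | 92.2% | 86.5% |

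All four stated powers match one-sided 5%, and none matches the 95% limit. With 150 events instead of 151, line 1 becomes 79.9% and 70.0%. In Table 3, the unrounded 94.6 events give 86.4% with the 95% limit; letting the 95 events split in proportion to the hazard ratio of 0.8 gives 86.1%. All of these are about 86%. Freedman's formula does not explain the stated figures: at one-sided 5% it needs 155 events for line 1.

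**Step 3: observation time for 80% power with the 95% limit.** 191 events / 0.001 = 191,000 WY, about 41,000 WY more than the 150,000 that 6.5 takes as the feasibility limit.

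**Step 4: largest observed hazard ratio that passes, at 150 events.** This is 1.5 × exp(−z_α × 2/√150).
- 95% interval: 1.5 × exp(−1.960 × 0.1633) = 1.09
- 90% interval: 1.5 × exp(−1.645 × 0.1633) = 1.15

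An estimate between about 1.09 and 1.15 would be non-inferior under one rule and not under the other.

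**The case against.** The strongest reply is that nothing has been miscalculated. The hypotheses point in one direction, α is 0.05, and a calculation with z = 1.645 agrees with both. The sentence that sets the decision rule gives no level, and the 95% interval comes later as a statement about how the estimate will be reported. On that reading the decision limit is a one-sided 95% limit and 80% is correct. Section 6.7.1 also defers a detailed analysis plan to the first year after study start, for approval by the Safety Monitoring and Advisory Council, and the level could be fixed there.

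Much of this stands, and it rules out three stronger readings that a reader might infer:

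- **That power simply is 70%.** This is conditional on the two-sided 95% limit deciding, which the protocol does not state.
- **That the power arithmetic is wrong.** All four figures are correct for a one-sided 5% test.
- **That the sponsor could freely move to a 90% interval once results are known.** The council-approved plan due in the first year reduces this risk, and 6.7.2 excludes modelling of the primary outcome from the interim reports.

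The reply does not remove the point. One-directional hypotheses do not fix the level: both one-sided 5% and one-sided 2.5% fit them. The decision is made through a confidence limit, and 95% is the only interval level the protocol gives for that hazard ratio, in the abstract directly before the hypotheses and again in 6.7.1. Nor is this only a detail left for the analysis plan. The protocol itself prints the powers, the decision rule and the interval, and read in the ordinary way these do not fit together.

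**Conclusion.** The sample size and the analysis text do not fit together as written. The powers of 80, 97, 82 and 92% hold for a one-sided 5% test. If the upper limit of the two-sided 95% interval decides, they are about 70, 94, 73 and 86%. The abstract's claim of sufficient power would then lack support at 80%, the claim of more than 80% power for a 1.65-fold risk would fail, and 80% power at margin 1.5 would need about 191 events.

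The result takes the protocol's event counts and 1:1 allocation as given and uses the Schoenfeld approximation, which recovers the stated events and woman-years to rounding. It ignores any variance inflation from the inverse probability weighting. It covers the four powers in Tables 2 and 3; the statement in 6.5 about excluding a 2.5-fold ATE risk gives no power figure and is not covered. The point matters because it concerns the primary hypothesis and can change the conclusion for an observed hazard ratio between about 1.09 and 1.15.

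**What to change.** State the one-sided significance level and the confidence limit that decides, together and in the same terms, in the abstract, 6.5 and 6.7.1, before outcome data are analysed. Either of two versions is coherent:

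- **(a) The two-sided 95% interval decides.** Say that the test is at one-sided 2.5%. Restate the powers as 70, 94, 73 and 86%. Revise the abstract's claim of sufficient power and the 6.5 sentence claiming more than 80% power to exclude a 1.65-fold risk.
- **(b) The test is at one-sided 5%.** Say that the decision uses the upper limit of the two-sided 90% interval (a one-sided 95% limit) and that the 95% interval is descriptive only. The stated powers then stand.

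Version (b) agrees with the existing calculation and changes no figure. Version (a) keeps the only interval the protocol now names, at the price of acknowledging lower power. Either way the cost is wording, plus four restated powers and the two revised claims under (a). No additional participants are needed.
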